6.2 Free-field threshold

The purpose of this test is to establish the hearing thresholds in free field through a speaker in front position (0 degrees azimuth) according to the so-called ascending or modified Hughson-Westlake method (Figure 10). The test shall be performed with the non-test ear blocked (in case of normal or near-normal hearing or a large asymmetry with the non-test ear having significantly better hearing thresholds). The signal to be used should be narrow band noise.

At Visit 1, free-field thresholds shall be measured for the unaided situation and with the BP110 Power Sound Processor on a Baha Softband.

At Visit 4, 6, 7 and 8 this measurement should be performed with the investigational device.

[figure not shown]

Figure 10. Free field front speaker position.

6.3 Speech recognition in quiet

The purpose of this test is to establish the test subject's word recognition score in quiet. The speech test in quiet shall be performed using phonetically balanced words presented in free field through a speaker from the front (0 degrees azimuth) (figure 10). The test material shall be monosyllabic words and presented at 50, 65 and 80 dB sound pressure level (SPL) and scores shall be recorded as % correct words at each presentation level. The test shall be performed with the non-test ear blocked (in case of normal or near-normal hearing or a large asymmetry with the non-test ear having significantly better hearing thresholds).

At Visit 1, the speech in quiet test shall be performed for the unaided situation and BP110 Power Sound Processor on a Baha Softband.

At Visit 4, 6, 7 and 8 this measurement should be performed with the investigational device.

6.4 Adaptive Speech recognition in noise

The purpose of this test is to establish the test subject's ability to recognise speech in the presence of background noise. The adaptive speech test in noise shall be conducted using validated lists of phonetically balanced sentences, with speech presented in free field from the front (0 degrees azimuth) and noise from the back (180 degrees azimuth) (figure 11). The noise shall be kept constant at 65 dB SPL, and the speech shall be adapted stepwise according to the software used to establish the speech-to-noise ratio (SNR) providing a 50% level of understanding. Software and speech material to be used is the Matrix test in language specific versions as applicable.

The test shall be performed with the non-test ear blocked (in case of normal or near-normal hearing or a large asymmetry with the non-test ear having significantly better hearing thresholds).

The speakers should be at the height of the test subjects head and more than 1 metre away from the test subject. There should preferably be more than 1 metre of free space around the test subject in all directions. This is in accordance with the current standard¹¹.

CBAS5539 CIP Version 5

[figure not shown]

Figure 11. Speech in noise test speaker position

At Visit 1, the speech in noise test will be performed for the unaided situation and BP110 Power sound processor on a Baha Softband. If the subject presents with hearing aids preoperatively, the measurement will also be completed in the subject's test ear in the aided condition.

At Visit 4, 6, 7 and 8 this measurement should be performed with the investigational device.

IMPORTANT: When all audiological tests have been performed and the audiological team is pleased with the data collection, remember to reset the sound processor features according to the patient's fitting.

6.5 Abbreviated Profile of Hearing Aid Benefit (APHAB form A)

The APHAB form "A" questionnaire from HARL (Hearing Aid Research Lab, University of Memphis, USA) is a 24-item self-assessment inventory that evaluates the benefit experienced by the subject when using hearing amplification compared to the unaided situation. APHAB produces a global score and scores for four subscales: ease of communication, reverberation, background noise, and averseness.

The subjects will complete the APHAB questionnaire at Visit 1, 6 and 8.

- At Visit 1, the subjects shall complete the questionnaire prior to the Softband test, and the questionnaire shall be answered with respect to an unaided hearing situation, even for subjects with a previous hearing device.
- At Visit 6 and 8, the subjects shall complete the questionnaire for the aided situation (with the Investigational device).

The APHAB questionnaire is available for free and in a number of different translations on the HARL home page.

6.6 Speech, Spatial, and Qualities of Hearing Scale (SSQ-12 version)

The short form of Speech, Spatial, and Qualities of Hearing questionnaire (SSQ-12) from MRC Institute of Hearing Research, UK, is a scaled-down version of the 49 items SSQ questionnaire. It is designed to compile a sub-set of items from the longer original 49 version to represent the scale as a whole, measuring self-reported auditory disability, reflecting the reality of hearing in the everyday world. It has been shown to provide similar results to SSQ49¹². It covers:

- Hearing speech in a variety of competing contexts
- The directional, distance and movement components of spatial hearing
- Segregation of sounds and attending to simultaneous speech streams
- Ease of listening
- The naturalness, clarity and identifiability of different speakers, different musical pieces and instruments, and different everyday sounds

The subjects will complete the SSQ questionnaire at Visit 1, 6 and 8.

- At Visit 1, the subjects shall complete the SSQ questionnaire prior to the Softband test and the SSQ questionnaire shall be answered with respect to an unaided hearing situation, even for subjects with a previous hearing device.
- At Visit 6 and 8, the subjects shall complete the questionnaire for the aided situation (with the Investigational device).

The SSQ-12 questionnaires was approved for use in this clinical investigation for free by the MRC Institute of Hearing Research.

6.7 Health Utility Index (HUI23)

The Health Utilities Index (HUI®) 23S15Q is a generic preference-based system for measuring comprehensive health status and health-related quality of life (HRQL). HUI provides descriptive evidence on multiple dimensions of health status, a score for each dimension of health, and a HRQL score for overall health. Health dimensions include vision, hearing, speech, ambulation/mobility, pain, dexterity, self-care, emotion and cognition. Each dimension has 3-6 levels. The version in this clinical investigation uses a recall time of 1 week.

The subjects will complete the HUI at Visit 1, 6 and 8.

- At Visit 1, the subjects shall complete the HUI questionnaire prior to the Softband test and with respect to their current hearing situation
- At Visit 6 and 8, the subjects shall complete the questionnaire for the aided situation (with the Investigational device).

The license to use the HUI questionnaire is purchased from Health Utilities Inc., [name].

6.8 Daily use

During the clinical investigation at visit 5, 6, 7 and 8 data regarding daily use of the sound processor will be collected.

CBAS5539 CIP Version 5

[figure not shown]
- Average hours of daily use (hours/day) during the last week before Visit 5, and during the last month before Visit 6-8.
- Softpad use (Yes/No) and if yes, frequency of change; number of times the subject changed the Soft pad during the last week before Visit 5, and during the last month before Visit 6-8?
- Comfort (by visual analogue scale 100 mm). Subject will be asked at Visit 5-8:

With regard to your Sound processor, please rate the overall comfort by placing a single vertical line on the scale.

Not comfortable *Most comfortable*
at all *imaginable*

6.9 Numbness

Sensibility of the skin directly over the implant is an important outcome measurement to establish a possible difference between surgery with or without skin thinning. Two different sensibilities will be tested by means of a broken wooden cotton swab/bud (q-tip): gnostic (with cotton side) and vital (with broken, sharp wooden side) sensibility. The measurement locations and procedures need to be standardized (Figure 12). ATB Implant site evaluations regarding numbness will be performed at Visits 3-8.

- 30 and 60 mm along the lines from the centre of the coil/magnet
- Cranial and caudal and 90 degrees anterior and posterior
- No sampling on the incision line
- The sequence of gnostic/vital stimuli randomly gently applied
- Gnostic sensibility :0-100% 8 locations
Vital sensibility: 0-100% 8 locations
Total sensibility: 0-100% 16 trials

Figure 12. ATB Implant site evaluation.

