10.6 Safety analyses

10.6.1 Implant site evaluation

Evaluation regarding numbness will be presented.

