3.2.2 Secondary Efficacy Variables/endpoints

- Abbreviated Profile of Hearing Aid Benefit (APHAB) at visit 1 (unaided), m 3, m 6 and m 12:
 - Global score
 - Ease of Communication
 - Reverberation
 - Background Noise
 - Aversiveness
- Thresholds audiometry: PTA-4, 250, 500, 1000, 2000, 3000, 4000, and 6000 Hz at visit 1, w 4, m 3, m 6 and m 12
- Speech perception in quiet (50dB, 65dB and 80dB SPL) at visit 1, w 4, m 3, m 6 and m 12
- Adaptive speech recognition in noise (50% performance) at visit 1, w 4, m 3, m 6 and m 12
- Feedback measurement at each frequency at visit w 4, w 6, m 3, m 6 and m 12
- Generic quality of life scale: Health Utility Index (HUI) at visit 1 (unaided), m 3, m 6 and m 12:
 - Health related quality of life score for overall health
 - Vision score
 - Hearing score
 - Speech score
 - Ambulation/mobility score
 - Dexterity score
 - Self-care score
 - Emotion score
 - Cognition score
- The Speech, Spatial and Qualities of Hearing Scale (SSQ) at visit 1 (unaided), m 3, m 6 and m 12

Surgical variables

- Soft tissue thickness (mm)
- Surgery time (time of first incision to time of last suture), (min)

Protocol:

Clinical performance of a new implant system for bone conduction hearing

Protocol No:

CBAS5539

Version:

1.0

Page 12 of
22

- Type of anaesthesia
- Soft tissue thinning performed
 - Yes
 - No
- Bone polishing/removal below the actuator site performed
- BI300 length
 - 3 mm
 - 4 mm
- Location of BI300 Implant
- Surgical incision/location

Questions about usage will be collected at w 6, w 12, m 6 and m 12:

- Daily use of sound processor (hours/day)
- Softpad use
- Question about comfort with the SP, using VAS, will be collected at w 4, w 6, m 3, m 6 and m 12.
- Magnet choice will be recorded at w 4, w 6, w 12, m 6 and m 12.

BC Direct thresholds at visit 1, w 4, w 6, m 3, m 6 and m 12

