3.3 Safety Variables/Endpoints

3.3.1 Implant site evaluation

Evaluation about numbness around the implant site will be performed at w 2, w4, w 6, m 3, m 6 and m 12.

- Total sensibility %
- Gnostic sensibility % (cotton swab) at 30 mm and 60 mm for Cranial, Caudal, Anterior and Posterior
- Vital sensibility % (sharp wooden) at 30 mm and 60 mm for Cranial, Caudal, Anterior and Posterior

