4.11.1 Implant site evaluation

Evaluation about numbness will be presented by visit. Changes from first measurement may be evaluated.

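### No planned output addresses the comparison of surgery with and without skin thinning that Protocol 6.9 gives as the reason for measuring numbness

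*Protocol*

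**What the plan says.** Protocol 6.9 treats sensibility of the skin over the implant as an important outcome, measured "to establish a possible difference between surgery with or without skin thinning". The test has 8 gnostic and 8 vital stimuli, each set scored from 0 to 100%, with a total over all 16. On timing, the protocol says "ATB Implant site evaluations regarding numbness will be performed at Visits 3-8". SAP 3.3.1 agrees: "Evaluation about numbness around the implant site will be performed at w 2, w4, w 6, m 3, m 6 and m 12". The first value is therefore taken two weeks after surgery.

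The grouping factor is collected. Protocol 5.7 records soft tissue reduction as yes or no during surgery, and SAP 3.2.2 lists "Soft tissue thinning performed" with the same two categories among the surgical variables.

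On analysis, Protocol 10.6.1 says only: "Evaluation regarding numbness will be presented". SAP 4.11.1 says: "Evaluation about numbness will be presented by visit. Changes from first measurement may be evaluated". SAP 4.1 puts numbness among the variables that are analysed descriptively only. The SAP table list has one numbness table, 14.3.2, for the Safety Population.

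**The concern.** Protocol 6.9 gives a reason for a 16-stimulus test repeated at six visits, and the reason is comparative. A by-visit summary over all subjects cannot show whether sensibility differs between those who had thinning and those who did not, because it averages over the two groups. A reader of the report who goes back to 6.9 will find the question asked and no output that bears on it, although both variables are in the database.

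There is a smaller labelling issue. With no pre-operative measurement, change from the first value is change since week 2 after surgery. A subject with sensory loss already present at week 2 and unchanged afterwards would score zero change.

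**Working it through.** The documents give no sample size, SD, meaningful difference or thinning split for numbness, so there is no figure to reproduce. The check is first a comparison of the text, then an illustration of how precise a split table could be.

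**Text check**

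| Step | Place | Finding |
|---|---|---|
| Purpose | Protocol 6.9 | Difference by skin thinning |
| Grouping variable | Protocol 5.7; SAP 3.2.2 | Recorded, yes/no |
| Formal objective | Protocol 4.3; SAP 1.1 | Numbness under implant site evaluations; thinning not mentioned |
| Analysis | Protocol 10.6.1; SAP 4.11.1 | Presented, by visit |
| Type of analysis | SAP 4.1 | Descriptive only |
| Output | SAP 7.1, Table 14.3.2 | Safety Population; no split by thinning in the title |
| General stratification | Protocol 10.4 | SSD versus Conductive/Mixed, and pooled; not thinning |

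No row joins numbness to thinning. This reads skin thinning (Protocol 6.9), soft tissue reduction (Protocol 5.7) and soft tissue thinning (SAP 3.2.2) as the same item.

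**Precision of a split table**

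Inputs: 50 subjects (Protocol 3.2). The split n1/n2 is assumed, and results are in units of the unknown SD, taken as common to both groups.

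SE of the difference in means = SD × sqrt(1/n1 + 1/n2). The half-width of a two-sided 95% interval = 1.96 × SE (normal approximation).

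| Assumed split | Variance term | SE (SD units) | 95% half-width (SD units) |
|---|---|---|---|
| 25/25 | 1/25 + 1/25 = 0.080 | 0.28 | 0.55 |
| 10/40 | 1/10 + 1/40 = 0.125 | 0.35 | 0.69 |
| 5/45 | 1/5 + 1/45 = 0.222 | 0.47 | 0.92 |
| 3/47 | 1/3 + 1/47 = 0.355 | 0.60 | 1.17 |

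Missing visits would widen all of these.

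**Number of contrasts**

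Three scores (total, gnostic, vital) at six visits would give 3 × 6 = 18 differences. Total sensibility alone gives 6.

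**The case against.** The strongest reply is that the SAP delivers what the protocol's statistical section asks for. Thinning appears in one introductory sentence of Protocol 6.9. It is absent from the objectives tables, from the statistical objectives in Protocol 10.1 and from the safety endpoints in 10.2.3. Protocol 10.6.1 asks only for presentation. This stands: the mismatch is between a stated rationale and the analysis. A reader might infer that a protocol objective has been dropped, or that this comparison is all the measurement was for. The documents support neither, since a by-visit description of implant-site sensation is a legitimate use of the data. Listing numbness first among the safety variables also gives it no rank over adverse events, device deficiencies or the audiogram.

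A reader might also infer that the SAP will report numbness as change from a post-operative value and so hide lost sensation. That does not hold. The change is optional, by-visit presentation is the only firm commitment, and the scores are absolute percentages of stimuli felt, so the level at each visit already shows how much sensation is present. Only the labelling point remains.

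The reply also bears on the remedy. Thinning is not randomised. Protocol 5.7 leaves the surgical procedure to the investigator's judgment, and about 10 subjects are planned at each of five clinics, so thinning may be mixed with tissue thickness, surgeon and site. Eighteen differences with intervals would sit badly with the descriptive-only rule in SAP 4.1. Both points stand and limit what should be added. They do not remove the gap, because a descriptive table can be split by thinning without a test.

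**Conclusion.** The point holds as a minor one. Protocol 6.9 names a comparison by skin thinning, the factor is recorded, and no planned analysis or table presents numbness by that factor. The primary efficacy analysis, the sample size and the go/no-go safety interim do not depend on it. No data are lost, since the table can be made from what is already collected.

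The size cannot be stated in sensibility points, because neither the SD nor the split is given. Under the assumed splits the standard error runs from 0.28 SD at 25/25 to 0.60 SD at 3/47, so the contrast may be too imprecise to settle the question in 6.9. With no randomisation and no pre-operative value, it would be exploratory at any split.

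**What to change.** 1. In SAP 4.11.1 and Table 14.3.2, keep the by-visit summary and add total, gnostic and vital sensibility by visit and by soft tissue reduction (yes/no), descriptively, with the number in each group.
2. For total sensibility only, give the difference in means with a confidence interval if both groups are large enough, with the minimum group size set in advance. Protocol 6.9 names no direction, so a two-sided interval fits better than the one-sided form in SAP 4.1. Amend the descriptive-only statement in SAP 4.1 to match.
3. Mark the comparison exploratory and non-randomised, open to confounding by soft tissue thickness, surgeon and site. Show soft tissue thickness by group alongside.
4. If the optional change score is reported, label it as change since week 2 after surgery.

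If the sponsor no longer wants the comparison, the alternative is to remove the comparative purpose from Protocol 6.9.

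The cost is an extension of one table from collected data and a short edit to SAP 4.1, with no new visits and no effect on the type I error of the confirmatory tests. The downside is a confounded and possibly imprecise estimate that could be over-read, which is why the group sizes and the caveat belong in the table itself.

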7 ADVERSE EVENT AND DEVICE DEFICIENCIES

7.1 Device deficiency reporting

The definition of a device deficiency is *"an inadequacy of a medical device with respect to its identity, quality, durability, reliability, safety or performance."*

Any a device deficiency observed will be fully investigated by the investigator and documented in the case report form (CRF).

A device deficiency that could have led to a Serious Adverse Event (SAE) should be reported immediately (see next section).

7.2 Adverse Event (AE) and Serious Adverse Event (SAE)

7.2.1 Definitions

| Term | Definition |
|--|---|
| Adverse Event (AE) | 
Any untoward medical occurrence, unintended disease or injury, or untoward clinical signs (including abnormal laboratory findings) in subjects, users or other persons, whether or not related to the medical device used in the investigation.
 
NOTE 1 This definition includes events related to the investigational medical device or the comparator.
 
NOTE 2 This definition includes events related to the procedures involved.
 |
| Adverse Event of Special Interest (AESI) | 
An AESI is an AE of scientific and medical concern specific to the sponsor's product(s).
 
The reporting requirements from the investigator to CBAS for an AESI will be the same as the reporting requirements for an SAE
 |
| Adverse Device Effect (ADE) | Adverse event related to the use of an investigational medical device |
| Serious Adverse Event (SAE) | 
Adverse event that
 
a) led to death
 
b) led to serious deterioration in the health of the subject, that either resulted in
 
 • a life-threatening illness or injury • a permanent impairment of a body structure or a body function • in-patient or prolonged hospitalization • medical or surgical intervention to prevent life-threatening illness or injury or permanent impairment to a body structure or a body function |

| | |
|---|---|
| | 
c) led to foetal distress, foetal death or a congenital abnormality or birth defect
 
Note - Planned hospitalization for a pre-existing condition, or a procedure required by the CIP, without serious deterioration in health, is not considered a serious adverse event.
 |
| Serious Adverse Device Effect (SADE) | Adverse device effect that has resulted in any of the consequences characteristic of a serious adverse event |
| Unanticipated Serious Adverse Device Effect USADE | Serious adverse device effect which by its nature, incidence, severity or outcome has not been identified in the current version of the risk analysis report |

7.2.2 Handling and reporting of AEs and ADEs

Subjects will be carefully monitored during the investigation for possible adverse events and appropriate treatment of the subject will be initiated.

Any adverse events observed will be fully investigated by the investigator and documented in the case report form (CRF) including assessment of seriousness, severity (mild, moderate or severe) and relationship to the medical device.

7.2.3 Definition of AESI in this clinical investigation

The following AEs are defined as adverse events of special interest (AESIs) and should be reported within 24 hours, after being aware of an event (see section 7.4.2.4):

- AE that interferes with the daily use of the medical device(s)
- AE at the site of the implant that leads to
 - Revision surgery including explantation
 - Severe soft tissue complication
 - Prescription of antibiotics

7.2.4 Clinically significant threshold shifts

Shifts in threshold, relative to the preoperative baseline, will be reported as an adverse event (AE) when a shift at any frequency exceeds 15 dB HL.

7.2.5 Handling and reporting of AESIs, SAEs and device deficiency that could have led to a SAE

An investigator should report within 24 hours, after being aware of the event, an AESI, SAE or a device deficiency that could have led to a SAE. The report shall be sent as an email attachment to the safety inbox or faxed to Cochlear Bone Anchored Solutions AB. Contact information is available on the SAE form.

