5.1 Test equipment

The test set-up regarding speaker placement, sound room facility and software used at each clinic shall be checked and approved by the Sponsor at the latest during the Site initiation visit. All tests shall be performed in the sound isolated room. Equipment used for audiological testing shall be calibrated before initiation of the investigation. Calibration certificates will be asked for by the Sponsor as part of the study documentation. It is important to keep the same sound room and test equipment set-up during the entire clinical investigation. Changes are not allowed.

If, for some exceptional reason, any significant changes would be needed with the test equipment during the investigation a new calibration needs to be performed together with a new unaided baseline measurement. Calibration documentation should be kept with the Investigator File.

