5.5 Audiogram

Unaided audiometric threshold measures (including both air- and bone conduction thresholds) should demonstrate that the subject has a conductive, mixed hearing loss or single-sided sensorineural deafness and meets the audiological inclusion criteria.

An existing audiogram may be used as long as it has been completed during the last six months, and contains all the required relevant frequencies (250, 500, 750, 1000, 1500, 2000, 3000, 4000, 6000 and 8000Hz). The subject's pre-operative Pure Tone Average PTA4 (mean of 500, 1000, 2000 and 4000Hz) should be computed and recorded to ensure the subject meets the inclusion criteria.

If an audiogram is older than 6 months or does not contain the required frequencies, a new will be performed at Visit 1. Frequencies required for air conduction thresholds are 250, 500, 750, 1000, 1500, 2000, 3000, 4000, 6000 and 8000Hz. Bone conduction thresholds are 250, 500, 750, 1000, 1500, 2000, 3000, 4000 and 6000Hz. Contralateral masking should be used if needed, and according to local practice. The hearing care professional shall always record the unmasked threshold and record the masked if applicable.

Audiograms for bone conduction thresholds will also be performed at Visits 6, 7, and visit 8 to monitor hearing thresholds postoperatively.

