6.1 Postoperative audiometric assessment

Bone conduction thresholds for the study ear will be monitored postoperatively, to characterize observed unaided thresholds postoperatively. These measures will occur at visit 6 (3 months postoperative) and 7 (6 months postoperative), once healing and swelling is most likely to be resolved and repeated at visit 8 (12 months postoperative). Bone conduction thresholds are 250, 500, 750, 1000, 1500, 2000, 3000, 4000 and 6000Hz. Contralateral masking should be used if needed, and according to local practice. The hearing care professional shall always record the unmasked threshold and record the masked if applicable.

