3.3.2 Adverse Events

Adverse events from visit 2 and onward will be presented.

- Adverse Event (AE) is all reported events
- Adverse Device Effect (ADE) is events that is Related to the device (Probably) or Related to the procedure (Probably)
- Serious Adverse Event (SAE) is events that has been marked as Serious
- Serious Adverse Device Effect (SADE) is events that has been marked as Serious and also marked as Related to the device (Probably) or Related to the procedure (Probably)
- The following AEs are defined as adverse events of special interest (AESIs):
 - AE that interfere with the daily use of the medical device(s)
 - AE at the site of the implant that lead to
 - Revision surgery including explantation
 - Severe soft tissue complication
 - Prescription of antibiotics

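### The safety baseline for the 15 dB bone-conduction shift rule may be an audiogram up to six months old with no equipment condition, and the rule leaves direction, masking and repeat testing open

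*Protocol*

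**What the plan says.** Protocol 7.2.4 is a single sentence. "Shifts in threshold, relative to the preoperative baseline", it says, "will be reported as an adverse event (AE) when a shift at any frequency exceeds 15 dB HL".

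The unaided audiogram after surgery is bone conduction only. It covers nine frequencies (250 to 6000 Hz) at Visits 6, 7 and 8, that is at 3, 6 and 12 months (Protocol 5.5 and 6.1). On masking, 6.1 says: "The hearing care professional shall always record the unmasked threshold and record the masked if applicable".

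On the baseline, Protocol 5.5 says: "An existing audiogram may be used as long as it has been completed during the last six months". The only other condition is that the required frequencies are present. For the study itself, 5.1 requires calibrated equipment and adds: "It is important to keep the same sound room and test equipment set-up during the entire clinical investigation". If a significant equipment change is unavoidable, "a new calibration needs to be performed together with a new unaided baseline measurement".

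Audiogram is a named safety variable (Protocol 4.3 and 10.2.3). In the SAP, section 3.3.2 says "Adverse Event (AE) is all reported events". Section 4.11.4 presents the audiograms by arm and defines no analysis of shifts.

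**The concern.** A threshold shift is a difference between two readings, so it is only as good as its baseline. Section 5.1 accepts that an unaided baseline is no longer valid once equipment changes significantly. Section 5.5 does not carry that reasoning over to an audiogram made before the study. Such an audiogram may come from another room or another audiometer, and it may be six months old at Visit 1. By the 12-month visit it would be at least 6 + 12 = 18 months old, plus the time from Visit 1 to surgery. A calibration difference or a change before surgery would then appear as a postoperative shift, or would hide one.

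The trigger also reacts to the most extreme of 9 × 3 = 27 comparisons per ear, with no repeat, so measurement noise accumulates. With both masked and unmasked values on file, two sites can apply the rule to different numbers. At stake is how the hearing-safety result of a new implant can be read.

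**Working it through.** **No plan figure to reproduce.** Neither document gives a test-retest SD, a false-flag rate or an expected number of shift AEs.

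**Inputs from the documents.** Criterion: more than 15 dB at any frequency (Protocol 7.2.4). Frequencies: 9 (6.1). Visits: 3 (5.5, 6.1). Comparisons per ear: 27. Subjects: 50 (3.2), one study ear each.

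**Assumptions, not in the documents.** No true change; normal test-retest differences with SD 4 to 8 dB; readings in 5-dB steps, so that exceeding 15 dB means 20 dB or more, a cut of 17.5 dB on the unrounded difference.

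**Formula, worsening only, independent comparisons.** p = 1 − Φ(17.5/SD), and P(at least one flag) = 1 − (1 − p)^27. At SD 6: p = 1 − Φ(2.917) = 0.00177, and 1 − (1 − 0.00177)^27 = 4.7%.

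**Simulation.** The three visits share one baseline, each reading is rounded to 5 dB, and the between-frequency correlation is 0 or 0.3. The last column requires one repeat at the same visit, with independent error, also to exceed 15 dB.

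| Assumed SD (dB) | p | Formula, 27 comparisons | Simulation, worsening | Of 50 subjects | Worsening confirmed on repeat |
|---|---|---|---|---|---|
| 4 | 0.000006 | 0.02% | under 0.1% | about 0 | under 0.1% |
| 5 | 0.00023 | 0.6% | about 1% | about 0.5 | under 0.1% |
| 6 | 0.00177 | 4.7% | 5-6% | about 3 | 0.4-0.5% |
| 7 | 0.00621 | 15.5% | 14-16% | 7-8 | about 2% |
| 8 | 0.01435 | 32.3% | 25-31% | 13-15 | 5-6% |

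Rounding each reading raises the simulated rate a little at small SD. The shared baseline and the correlation lower it at large SD.

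**Effect of a baseline offset (illustration).** Take SD 5 dB and an assumed offset of one 5-dB step.
- Old equipment reads 5 dB too good at all nine frequencies: the cut falls to 12.5 dB, p = 1 − Φ(12.5/5) = 0.0062, and 1 − (1 − 0.0062)^27 = 15.5%, against 0.6% without the offset.
- Old equipment reads 5 dB too poor, and the ear truly worsens by 20 dB at one frequency: the chance of a flag at one visit is 1 − Φ((17.5 − 15)/5) = 31%, against 1 − Φ((17.5 − 20)/5) = 69% without the offset.

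An offset can therefore create flags or hide real losses. Re-measuring at follow-up does not remove it, because all three visits use the same baseline.

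**The 6-month audiogram.** Protocol 4.3, 5.5 and 6.1 schedule bone conduction at 3, 6 and 12 months. SAP 3.3.4 collects it at 3 and 12 months, and SAP 4.11.4 and the audiogram tables in 7.1 cover Visits 1, 6 and 8. SAP 4.2 puts the primary safety analysis at 6 months, and SAP 6 declares no changes from the protocol. These sections contradict each other.

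**The case against.** **Improvements.** Because 7.2.4 names no direction, a reader might infer that a 20 dB gain must be reported as an AE. The documents do not support that. The section heading speaks of clinically significant shifts, and 7.2.1 confines an AE to something untoward. Worsening is the natural reading, and what is missing is the word.

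**Other equipment.** A reader might infer that baselines will come from other equipment. No section says so, and 5.1 shows the intent to keep the set-up constant. Other equipment is only not excluded.

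**Device effects.** A flagged shift does not become an adverse device effect automatically. Protocol 7.2.2 requires the investigator to assess relationship, and SAP 3.3.2 counts only events probably related to device or procedure.

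**Masking.** Masked values are recorded where needed, so a like-for-like comparison is possible. In the SSD arm the implanted ear is already deaf, which limits what an unmasked value could hide there. The rule still does not say which value to compare.

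**Consequences.** AEs are only described (SAP 4.1), shifts are not among the listed events of special interest on which the interim go/no-go focuses, and bone-conduction thresholds are also shown separately by arm. A sensitive trigger is a defensible choice for a new implant. That stands, and it is a reason to keep reporting unconfirmed shifts. It does not help with the baseline, because the separate audiogram display uses the same preoperative values.

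**Conclusion.** The point holds for the baseline. Section 5.5 permits, for a named safety endpoint, a reference measurement with no equipment condition and up to six months of age, while 5.1 treats a significant equipment change as requiring a new unaided baseline. The resulting bias can go either way, and its size cannot be known from the documents.

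The missing direction, masking choice and repeat test are gaps in wording. It would be tempting to conclude that many AEs will be pure noise. The documents do not support this: the chance-worsening rate runs from under 0.1% at an SD of 4 dB to about 25-31% at 8 dB, and the SD is an assumption throughout. The change is worth making because it is cheap, not because a large error has been shown.

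**What to change.** - **Protocol 5.5:** accept an existing audiogram for eligibility only. Take the safety baseline from bone-conduction thresholds at the nine frequencies, measured at Visit 1 on the study equipment.
- **Protocol 7.2.4:** keep the 15 dB figure. State that the shift is a worsening of the bone-conduction threshold in the implanted ear, and compare masked with masked where masking was applied. Repeat a flagged frequency at the same visit and record the result. Continue to report every flagged worsening as an AE.
- **SAP 4.11.4:** tabulate confirmed and unconfirmed shifts separately, by visit and arm.
- **Reconcile** the 6-month audiogram between Protocol 4.3, 5.5 and 6.1 and SAP 3.3.4, 4.11.4 and 7.1.

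The cost is wording in both documents, nine thresholds at Visit 1 for subjects who would have used an old audiogram (a visit that already includes audiometry), and a short repeat for each flagged frequency. The downside is a few extra minutes of testing for those subjects. Because unconfirmed shifts are still reported, AE capture loses nothing.
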